16. STATISTICAL ANALYSIS PLAN

To assess differences in clinical and demographic variables of the patients allocated to the two study groups, independent samples t test or Mann–Whitney U test will be used for quantitative variables. For categorical variables, Chi-square test or Fisher's exact test will be used. Outcome analysis will be performed using both an intention to treat analysis and a per-protocol analysis.

The overall impact of the intervention on the primary and secondary outcomes will be assessed considering both the results at the 8-week assessment as well as change from baseline.

Differences between interventions will be evaluated using independent samples t test or Mann-Whitney U test. For non-normally distributed variables, the magnitude of the difference in the medians will be assessed using Hodges-Lehman estimator. Additionally, a repeated measures ANOVA will also be performed, with group as an independent factor and time as a within-subjects factor. When necessary, logarithmic transformation will be performed to obtain normally distributed variables. In all analysis, a significant level of 0.05 will be considered.

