9. SAMPLE SIZE ESTIMATION

Sample size estimation calculations were performed taking into consideration the primary outcome measure – the QuickDASH. In a sample of 57 patients with shoulder tendon disorders treated with SWORD Health's medical device in the context of work-related conditions, the mean and standard deviation of the QuickDASH scale at baseline was of 59 and 19 points respectively. A Minimal Detectable Difference (MDD) of 11.2 points was considered, based on the psychometric properties of the scale.⁵⁶ Considering a power of 80%, a two-sided 0.05 significance level and a 10% dropout rate, 80 (40+40) patients would be necessary to detect a 11.2 points difference between the two groups.

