15. PARTICIPANT ASSESSMENTS

Patients will be assessed at baseline, 4 and 8 weeks.

Baseline Assessment

This assessment will involve a face-to-face visit, where the following information will be collected:

- a) date of birth
- b) gender
- c) height & weight
- d) body mass index
- e) formal education (years of schooling)
- f) job type
- g) previous shoulder surgery (> 3 months ago)
- h) Working status
- i) Geocodes/zip
- j) Race/ethnicity
- k) Age

The following outcomes will also be assessed in this visit: a) Shoulder Range of Motion; b) PROMIS CAT measures.

Shoulder Range of Motion will be measured in the following movements: 1) shoulder flexion; 2) shoulder abduction; 3) external rotations with shoulder abducted at 90 degrees. The participant will be asked to perform three non-painful repetitions of each movement, in a standing position. The investigator will measure the maximum joint angle attained by the participant, using a digital goniometer in each repetitions. The highest of the three values will be considered.

Regarding satisfaction with social role and ability to participate in social roles and activities, these will be collected through PROMIS CAT v2.0. These will be collected onsite, and the results will then be transferred by the investigator to the eCRF.

Assessment of primary outcome, as well as the remaining secondary outcomes will be performed through an electronic questionnaire to be filled by participants, through the EDC system. These will need to be filled within 5 consecutive days, counting from the date they are sent to the participant. To promote compliance with this schedule, whenever the deadline is approaching, automatic email reminders will be sent to participants. Participants will be excluded from the study

for protocol breach in case they don't fill in the assessment forms. Upon completion of the baseline form, participants in the study will receive a stipend of \$25.

Additional measurements of upper limb function and tri-dimensional motion will also be performed at the onsite visit by the clinician, using a motion capture system. These will not be considered in the outcomes of this study, but will be made available for post-hoc analysis.

Interim assessment (4 weeks)

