Participants will be required to complete a questionnaire similar to the baseline assessment, within a 5-day window beginning at the start of week 4. These assessments will include all the information pertaining to the primary and secondary outcomes, except for those that are collected through a face-to-face assessment. These (shoulder range of motion and PROMIS CAT measures) will not be collected on this assessment. Upon completion of this form, participants in the study will receive a stipend of \$25.

Final assessment (8 weeks)

This assessment will involve a face-to-face visit, where the following outcomes will be assessed: a) shoulder Range of Motion; b) PROMIS CAT measures and c) Participant satisfaction (Net Promoter Score). Shoulder Range of Motion and PROMIS CAT measures will be assessed using a similar methodology to the one descried for the baseline assessment.

Participants will also be required to complete a questionnaire similar to the baseline and interim assessments, within a 5-day window beginning at the start of week 4. These assessments will include all the information pertaining to the primary and secondary outcomes, except for those that are collected in the face-to-face visit. Upon completion of this form, participants in the study will receive a stipend of \$25.

Additional measurements of upper limb function and tri-dimensional motion will also be performed at the onsite visit by the clinician, using a motion capture system. These will not be considered in the outcomes of this study, but will be made available for post-hoc analysis.

Engagement assessment

For participants on the digital group, engagement and usage metrics of the educational and CBT components will also be collected automatically.

Additionally, the following activity log will be collected from patient's Electronic medical records and time stamps, as well as paper survey (or, in the case of the digital group, sent to the study coordinator via email, with the participant identified only by the study ID), to be entered into EDC portal by study coordinator:

- 1. Face-to-face visits registry (dates, times and duration)
- 2. Remote sessions registry (dates, times and duration)
- 3. Number and duration of contacts between PT and participant (emails, text messages, phone and videocalls)
- 4. Total time spent on remote monitoring of the patient (digital group only)

Adverse events

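### The plan promises intention to treat but does not define the set, names no method for missing scores, and does not use the 4-week QuickDASH to correct for loss

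*Combined protocol and SAP*

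**What the plan says.** Section 16 (Statistical Analysis Plan) states: "Outcome analysis will be performed using both an intention to treat analysis and a per-protocol analysis". It does not say who belongs to the intention-to-treat set or what happens when a score is missing. Results are assessed "considering both the results at the 8-week assessment as well as change from baseline". For the comparison of the arms, the section states: "Differences between interventions will be evaluated using independent samples t test", with a Mann-Whitney test as the alternative. In addition, "a repeated measures ANOVA will also be performed, with group as an independent factor and time as a within-subjects factor"; the section does not say which visits enter or how incomplete records are treated.

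Section 15 (Participant Assessments) sets the visits: "Patients will be assessed at baseline, 4 and 8 weeks". Of the 4-week questionnaire it says: "These assessments will include all the information pertaining to the primary and secondary outcomes, except for those that are collected through a face-to-face assessment". QuickDASH is a questionnaire outcome, so it is collected at 4 weeks.

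Three other places bear on loss:
- Section 9 (Sample Size Estimation) allows for "a 10% dropout rate".
- Section 15, under the baseline assessment, removes participants who leave their forms unfilled. Whether this reaches the later forms is unclear.
- Section 14 (Intervention) labels participants as dropouts by a different inactivity rule in each arm. It does not say whether they are still sent the 8-week form.

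**The concern.** An intention-to-treat comparison should cover everyone randomised, in the allocated arm. As written, the between-arm tests can cover only those who returned an 8-week form, and no other text supplies a way to bring the rest in. Inflating the sample for dropout protects precision but does not remove bias.

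The trial is unblinded and compares home exercise with clinic visits, so the amount of loss and its link to early response could plausibly differ by arm. A comparison of completers then flatters the arm that loses more poor responders. This matters more because the hypothesis in section 6 is that the digital programme does at least as well as conventional PT. The 4-week score is the best available information on people lost later, and the plan makes no use of it for this purpose.

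**Working it through.** **Numbers analysed.** The plan's 80 (40+40) with 10% loss leaves 40 × 0.9 = 36 per arm with an 8-week score. (The stated two-sided inputs do not reproduce 80: they give 46 per arm, 52 after loss, 104 in all. A one-sided 0.05 test gives 36, 40 and 80. That is a separate matter and nothing below depends on it.) If a further 5% to 10% miss only week 4, a classical three-visit ANOVA keeps 80 × 0.9 × 0.95 = 68.4 down to 80 × 0.9 × 0.9 = 64.8, or about 65 to 68 of 80. The t test and Mann-Whitney test still keep those people.

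**Bias among completers.** From the documents: SD 19, 40 per arm, 10% overall loss. Assumed: no true effect; correlations 0.60 (baseline to week 4), 0.75 (week 4 to week 8) and 0.51 (baseline to week 8); unequal splits of loss; and loss driven by a poor 4-week score, logit P(lost) = a + b·z4, with b from 1 to 3 per SD and a set to give each loss rate. Differences are digital minus conventional with a higher score taken as worse, and digital is assumed to lose more.

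Because loss depends only on the 4-week score, the bias follows from the shift in the 4-week mean among those kept:
- 8-week score: bias = 0.75 × shift.
- Change from baseline: bias = (0.75 − 0.60) × shift = 0.15 × shift, one fifth of the 8-week bias.

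| Loss, digital/conventional | 8-week bias (simulated) | Change bias (× 0.2) |
|---|---|---|
| 10%/10% | 0 | 0 |
| 12%/8% | −0.5 to −0.8 | −0.10 to −0.16 |
| 15%/5% | −1.2 to −2.1 | −0.24 to −0.42 |
| 20%/5% | −1.8 to −3.0 | −0.36 to −0.60 |

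For scale, the standard error at 36 per arm is 19 × √(2/36) = 4.5 points. In the 15%/5% and 20%/5% scenarios the 8-week test has a false-positive rate of roughly 5% to 10%, rising with b; the change-score test stays near 5%. Adjusting completers for baseline alone leaves −0.8 to −1.3 (15%/5%) and −1.1 to −1.9 (20%/5%). Using the 4-week score as well leaves about 0.1 or less.

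**What the ANOVA estimates.** Suppose the effect builds linearly (0, 5.6, 11.2 points), with 36 per arm, SD 19, a common between-visit correlation r of 0.4 to 0.7, and baseline counted as a level of time.
- Group effect: (0 + 5.6 + 11.2)/3 = 5.6. The SD of a three-visit mean is 19 × √((1 + 2r)/3) = 14.7 to 17.0. The non-centrality is 5.6/(SD × √(2/36)) = 1.61 to 1.40, so power is 36% to 28%.
- Group-by-time, 2 df: deviations −5.6, 0, 5.6, with sum of squares 62.72. λ = (36/2) × 62.72/(361 × (1 − r)) = 5.2 to 10.4, so power is 51% to 82%.

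The group effect averages in a pre-treatment visit, and the interaction is a 2-df test of any departure from parallel profiles. Neither is the 8-week contrast.

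**The case against.** The strongest reply is that much of this is read from silence. Section 16 neither states a complete-case analysis nor rules out imputation. That is correct, so a reader who infers that the plan has chosen a completers' analysis goes too far. What stands is that the tests it names cannot use a participant without an 8-week score and that nothing else is named.

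A reader might also infer that any missing form removes a participant from every test. It does not: missing week 4 alone leaves the t test and Mann-Whitney test untouched. Nor is the 4-week score necessarily unused, since it may enter the ANOVA; but a classical ANOVA deletes incomplete records and so does not correct for loss.

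On size, section 8.1 frames the primary outcome as running from baseline to 8 weeks, and for change the bias is small. That stands for loss driven by the 4-week level; loss driven by lack of improvement could bias change more. The unequal splits are assumptions, and equal loss gives no bias. Reminders and a payment per form should also limit missing forms.

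Finally, the 28% to 36% power for the ANOVA group effect should not be read as the power of the whole ANOVA. The interaction does better, the plan does not say which term will be interpreted, and the ANOVA is only an additional analysis.

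**Conclusion.** The point holds as a gap in the analysis plan that should be closed. The intention-to-treat set and the handling of missing scores are unspecified, the named methods cannot include everyone randomised once scores are missing, and section 15's removal rule and section 14's dropout labels may take away the data that an intention-to-treat analysis needs.

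The likely bias is modest. In the 15%/5% and 20%/5% scenarios it is 1.2 to 3.0 points on the 8-week score, or 11% to 27% of the 11.2-point target (1.2/11.2 and 3.0/11.2), and about 0.25 to 0.6 points on change. All of this rests on assumed correlations, loss splits and strength of dependence. The documents do not show that loss will be unequal, or which arm would lose more; if the conventional arm did, the sign would reverse. They therefore do not support a conclusion that the result will be biased towards the digital arm. They do support using a method that is protected if loss is unequal, since the score it needs is already collected.

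**What to change.** 1. Define the intention-to-treat set as all randomised participants, analysed by allocated arm.
2. Reconcile section 15's removal of participants with unfilled forms with that definition, and say which forms it covers.
3. State that the 4- and 8-week questionnaires are sought from everyone, whatever their adherence or dropout label. Also reconcile the final questionnaire's completion window, which section 15 starts at week 4, with the 8-week endpoint.
4. Replace the intention-to-treat 8-week t test and the repeated measures ANOVA with a linear mixed model of QuickDASH at 4 and 8 weeks. Terms are arm, visit, arm-by-visit and baseline-by-visit, with unstructured covariance and Kenward-Roger degrees of freedom. Report the 8-week arm difference with its 95% CI.
5. Report by arm how many participants have no post-baseline score, because this model cannot use them. Include them in a delta-adjusted multiple-imputation sensitivity analysis that worsens missing digital-arm scores in steps from 0 to 11.2 points.

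The cost is protocol and SAP wording, some programming, and follow-up effort for forms already scheduled; no new measurements are needed. The downside is that the model assumes missingness is explained by observed scores, which the delta analysis tests.

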8.2 Secondary Outcomes

The secondary outcomes will include the following:

a) Impact on shoulder range of motion

Shoulder range of motion will be measured in the following exercises: shoulder flexion; shoulder abduction and external shoulder rotation at 90 degrees of abduction.

b) Impact on Pain

Measured through the following question: "On a scale of 0 to 10, where 0 is no pain and 10 the worst pain imaginable, how would you rate your pain in the last 24 hours?"

c) Interest in undergoing surgery

Measured through the following question: "On a scale of 0 to 10, where 0 is not at all and 10 is extremely interested, how interested are you in undergoing shoulder surgery in the next 12 months"?

d) Medication consumption

Measured through the following questions:

- i. "Are you taking any medication for your shoulder pain?";
- ii. "If yes, on how many days in a week, on average, are you taking medication for your shoulder pain"

e) Impact on fear avoidance beliefs

Measured by: Patient-reported questionnaire (Fear Avoidance Beliefs Questionnaire- FABQ)

f) Impact on anxiety and depression

Measured by the General Anxiety Disorder-7 scale and Patient Health Questionnaire-9 scale

g) Impact on work productivity and activity impairment

Measured through Work Productivity and Activity Impairment Questionnaire: Specific Health Problem v2.0 (WPAI:SHP)

h) Satisfaction with social roles and discretional social activities

Measured through the Patient Reported Outcomes Measurement Information System Computerized Adaptive Test (PROMIS-CAT) scales: Ability to participate in social roles and activities (version 2.0) and satisfaction with social roles and activities (version 2.0).

i) Patient engagement

Measured through: g.1) adherence to exercise sessions; g.2) drop-out rates; g.3) treatment intensity (i.e. total number of exercise minutes)

j) Patient satisfaction

Measured through the Net Promoter Score, by asking participants the following question: "On a scale from 0 to 10, how likely are you to recommend this program to a friend or colleague?"

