14. INTERVENTION

a. Digital program

Patients in the digital intervention group will benefit from an 8-week program composed of therapeutic exercise, education and cognitive behavioural therapy (CBT) program provided by SWORD Health. These patients will be referred to SWORD Health by the investigator who identified the candidate. SWORD Health will then assign a physical therapist to each patient. The physical therapist will contact the patient for onboarding and will manage the case.

Patients in this group will performed home-based rehabilitation sessions using SWORD Phoenix[®], under remote monitoring by a physical therapist. Participants will be provided with a tablet computer with a SWORD mobile app installed, along with two inertial motion trackers (each comprised of a gyroscope, an accelerometer and a magnetometer) to be placed on chest, upper arm and wrist, respectively. These trackers enable precise movement quantification, feeding the mobile app, which guides the patient through the session, providing video and audio instructions before each exercise, as well as real-time audio and video biofeedback during the exercise. On the other end, the clinical teams are allowed to remotely monitor results and prescribe/edit exercise sessions through a web-based portal.

The exercise component will follow the protocol outlined in **Annex 2**, which can however be adapted by the physical therapist to the specific needs of the participant. Participants will be asked to start with three 20 min sessions per week, building gradually to three 30 min sessions per week. Participants will not be excluded from the study in case of lower adherence, but will not be included in the per-protocol analysis if they perform less than 21 sessions over the course of 8 weeks.

Participants in this group will be considered as dropouts if they: a) choose to abandon the study;b) do not engage in any exercise session for at least fourteen consecutive days.

The educational component will be delivered automatically through a smartphone app (available for iOS and Android), and will take the form of small educational texts that will be released

periodically to the participant. This component is not mandatory per protocol, but metrics on user engagement will be measured.

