The CBT program will take the form of a self-paced program consisting of written and prerecorded audio materials. An email will be sent weekly by the physical therapist to the participant, during the 8 weeks of the program. Each email will contain an introductory text describing the objectives for that week, as well as a link to that week's audio session and a PDF attachment with self-guided exercises. The CBT component is not mandatory per protocol, but metrics on user engagement will be measured.

b. Conventional PT

Patients in this group will benefit from a 8-week program consisting of two 30 min face-to-face PT sessions per week in an outpatient clinic setting, for a total of 16 sessions. The program will follow the principles outlined in **Annex 3**, which includes commonly used interventions adapted by the physical therapist to the specific needs of the participant.

Participants in this group will be excluded from the per protocol analysis if they complete less than 14 sessions over 8 weeks. Participants in this group will be considered as dropouts if they: a) choose to abandon the study; b) miss four consecutive scheduled PT sessions.

In addition to the face-to-face sessions, PTs will also be communicating with participants in this group through a secure messaging system (Mychart) used at UCSF or, alternatively, through a telephone check-ins (10-15 min calls, up to twice per week).

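### Section 16 does not exempt the engagement outcomes from the per-protocol analysis, so session adherence would be compared in a set selected on completed sessions

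*Combined protocol and SAP*

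**What the plan says.** Section 16 sets the analysis populations in one general sentence: "Outcome analysis will be performed using both an intention to treat analysis and a per-protocol analysis". The next paragraph gives the scope: "The overall impact of the intervention on the primary and secondary outcomes will be assessed considering both the results at the 8-week assessment", and also change from baseline. No outcome is excluded from either set.

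Section 8.2(i) makes patient engagement a secondary outcome, measured through "adherence to exercise sessions; g.2) drop-out rates; g.3) treatment intensity (i.e. total number of exercise minutes").

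Section 14 defines the per-protocol set separately by arm, on session count alone. Digital participants "will not be included in the per-protocol analysis if they perform less than 21 sessions over the course of 8 weeks". For the conventional arm: "Participants in this group will be excluded from the per protocol analysis if they complete less than 14 sessions over 8 weeks".

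Section 14 also defines drop-out, apart from the per-protocol rule. In both arms a participant who chooses to leave is a drop-out. So is a digital participant with no exercise session for fourteen days in a row, and a conventional participant who misses four scheduled sessions in a row.

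**The concern.** Adherence to exercise sessions is a function of the number of sessions completed, and that number decides who enters the per-protocol set. Comparing adherence between arms within the set conditions on the outcome being compared. Whatever the true difference, both arms must show high and similar adherence, because patients with low adherence have been removed. Drop-out and minutes are linked to session count as well, so they are affected, but less completely.

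Engagement matters for this intervention. Section 2 credits the earlier results with the device partly to high patient engagement, and the hypothesis in section 6 is that the digital program does at least as well as conventional PT. A per-protocol table with both arms in the mid-nineties for adherence and almost no drop-out would look like support for that hypothesis while carrying almost no information on it.

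**Working it through.** **Inputs from the documents**

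- Digital schedule (section 14a): "start with three 20 min sessions per week, building gradually to three 30 min sessions per week". Over 8 weeks this is 3 × 8 = 24 sessions. The total of 24 is inferred; the plan does not state it.
- Conventional schedule (section 14b): "two 30 min face-to-face PT sessions per week in an outpatient clinic setting, for a total of 16 sessions". Check: 2 × 8 = 16, as stated.
- Per-protocol minimum: 21 sessions (digital), 14 sessions (conventional).

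The plan gives no expected adherence and no adherence denominator, so there is no planned figure to reproduce.

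**Step 1. Adherence.** The floor is the per-protocol minimum divided by planned sessions.

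- Conventional: 14/16 = 87.5%. Only 14, 15 or 16 of 16 sessions are possible.
- Digital: 21/24 = 87.5%, if 24 is the denominator.

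**Step 2. Drop-out.**

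- Conventional, four consecutive misses: at most 16 − 4 = 12 sessions, below 14. No attendance pattern with two or fewer misses contains such a run, so this limb is empty unless sessions are made up.
- Digital, a 14-day gap on schedule: 24 − (2 × 3) = 18 sessions, below 21. A patient who averages 21/6 = 3.5 sessions a week in the other six weeks still qualifies.
- Leaving by choice: by the end of week 7 a fully adherent patient has 3 × 7 = 21 or 2 × 7 = 14 sessions. Someone who leaves in week 8 can be both a drop-out and in the per-protocol set.

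Per-protocol drop-out is therefore close to zero, with identifiable exceptions.

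**Step 3. Exercise minutes at planned session length.**

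- Conventional: 14 × 30 = 420 to 16 × 30 = 480 minutes.
- Digital: the floor lies between 21 × 20 = 420 and 21 × 30 = 630 minutes, depending on how fast sessions lengthen. No upper limit is stated.

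Minutes are truncated from below but can still differ between arms.

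**Step 4. Size of the distortion in adherence (assumed inputs).** Let each patient's attendance probability follow a beta distribution with mean m and concentration k, and let sessions attended be binomial out of 24 or 16. Per-protocol adherence is E[X | X ≥ c]/K, with c = 21, K = 24 (digital) and c = 14, K = 16 (conventional). The values of m and k are assumptions; none comes from the documents. Exact beta-binomial results:

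| Assumed mean, digital v conventional | k | Gap, all randomised | Share in per-protocol set | Per-protocol adherence | Per-protocol gap |
|---|---|---|---|---|---|
| 70% v 85% | 4 | 15 points | 30% v 64% | 93.6% v 95.9% | 2.3 points |
| 85% v 70% | 4 | 15 points | 62% v 33% | 95.8% v 93.6% | 2.2 points |
| 80% v 60% | 3 | 20 points | 53% v 22% | 95.6% v 93.4% | 2.2 points |
| 60% v 80% | 3 | 20 points | 20% v 55% | 93.4% v 95.7% | 2.3 points |
| 90% v 70% | 8 | 20 points | 74% v 25% | 95.7% v 92.1% | 3.6 points |

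For the 15-point gaps, k from 2 to 8 gives 1.8 to 2.6 points. For the 20-point gaps, including 70% v 90%, the same range of k gives 2.0 to 3.9 points. The shrinkage does not depend much on the assumed spread or on which arm adheres better.

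**The case against.** The strongest reply is that section 16 never names engagement. The sentence mentioning secondary outcomes concerns 8-week results and change from baseline, and a repeated measures ANOVA over time follows. Adherence, drop-out and total minutes have no baseline value, and section 15 describes engagement data under their own heading. The paragraph can be read as written for clinical outcomes only. This reading is fair, but the text does not say so. As worded, an analyst could produce the per-protocol engagement table and be following the plan.

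A reader might also infer more than the documents support:

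- *That the set is defined by all three engagement measures.* It is defined by session count only. Drop-out has its own definition, and minutes are not a criterion.
- *That per-protocol drop-out and minutes are fixed in advance.* Steps 2 and 3 show that drop-out can occur and that minutes can vary, most clearly in the digital arm.
- *That a real difference in engagement would be hidden.* The sentence that orders the per-protocol analysis also orders the intention-to-treat analysis, which shows the full gap.

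The digital denominator is a further fair challenge. Annex 2 heads its schedules as daily sessions, section 14a asks for three a week, and the therapist may adapt the protocol. If seven sessions a week were the denominator, the floor would be 21/56 = 37.5%, and a 14-day gap would leave 56 − 14 = 42 sessions, above 21. The digital figures in steps 1, 2 and 4 therefore hold only on the three-a-week reading. The conventional figures do not depend on it. The two places need to be reconciled.

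**Conclusion.** The concern holds for adherence. As written, the plan calls for a per-protocol comparison of an outcome on which the per-protocol set is selected. The 87.5% floor is certain in the conventional arm if missed sessions count against the stated 16. It holds in the digital arm if the denominator is 24. On those schedules drop-out in the set is near zero, and minutes are bounded below but not determined.

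Under assumed mean adherence of 60% to 90%, with digital sessions capped at 24, a true gap of 15 to 20 points would appear as about 2 to 4 points. The range rests on the beta-binomial assumption, but the direction follows from the selection rule.

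The consequence is limited. The intention-to-treat comparison of engagement is valid, and the QuickDASH analysis and the sample size are unaffected. What remains is an uninformative second result that could be reported as equal engagement.

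**What to change.** Add one sentence to section 16: adherence, drop-out and exercise minutes (section 8.2(i)) are compared in all randomised patients only, and the per-protocol analysis applies to QuickDASH and the other clinical outcomes.

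Section 8.2(i) should also state the adherence denominator for each arm, once section 14a and Annex 2 have been reconciled on the number of digital sessions.

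Reporting the share of each arm that enters the per-protocol set would help readers judge the per-protocol clinical results, but it is a reporting preference and not needed to remove the circularity.

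The change needs no new data and no more patients, and it leaves the primary analysis as it is. The only result lost is one that says almost nothing.
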